A sample of 1400 women will be recruited to the study. The sample size was based (at the time of grant application and original protocol development) on the 'rule of thumb' that 10 events (cases of the outcome) were required for each variable included in a multi-variable model to predict an outcome (20, 21). However, recent developments in prognostic model research have allowed us to confirm the above sample is sufficient for this study (22). The sample size calculation is based on a maximum of 7 variables being included in the model based on previously published validated prognostic models in pregnancy including between 1 and 7 predictor variables (23, 24, 25) and the least common pregnancy outcome, which is preeclampsia (estimated prevalence of approximately 5-6% of pregnancies in the UK) (26). Targeting a shrinkage factor of $\leq 10\%$ and C-index equal to 80%, we would need a minimum sample of 980 participants for a new model development for pre-eclampsia. Given that other outcomes are more prevalent than pre-eclampsia, they would require sample sizes smaller than the above figure.

f. Data collection

Following informed consent, participants' 12-week scans will be performed by the study sonographer. Once viability of the pregnancy and normal fetal anatomy is confirmed, the additional ultrasound adiposity measures needed for the study will be performed by the study sonographer. After ultrasound and any other clinical procedures are completed, the rest of the data collection will be performed by a female member of the research team, in a private room. Any women who do not consent to participating in the research will still have their 12-week scan carried out as planned, but no further measurements specific to the research will be taken.

Adiposity measures

The following ultrasound and anthropometry measurements will be taken.

Ultrasound scans:

- *Subcutaneous abdominal fat volume*
- *Visceral abdominal fat volume*
- *Total abdominal fat*

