The table provided in Appendix 2 indicates which additional predictor variables are available from routine records and which will be collected by questionnaire during the 12-week scan appointment. A member of the research team will be available to answer any queries that the participants have related to the completion of the questionnaire.

Outcomes

Adverse outcomes of interest are:

- Gestational diabetes; defined as fasting plasma glucose level of ≥ 5.6 mmol/litre or 2 hour plasma glucose level of ≥ 7.8 mmol/litre

- Gestational hypertension; defined as blood pressure $\geq 140/90$ mmHg on two occasions at least 4 hours apart after 20 weeks' gestation
- Preeclampsia; defined as a new onset of hypertension (>140 mmHg systolic or >90 mmHg diastolic) after 20 weeks of pregnancy with a new onset of proteinuria or/and maternal organ dysfunction or/and uteroplacental dysfunction. Early onset defined as onset of PE before 34 weeks gestation.
- Metabolic syndrome: diagnosed using 3 of the following measures: overweight/obese BMI or high waist circumference, elevated triglycerides, high blood pressure that's consistently 140/90mmHg or higher, insulin resistance.
- Pre-term birth; defined as birth before 37 weeks gestation
- Late-term birth; defined as pregnancy that extends over 41 weeks gestation
- Induction of labour; defined as non-surgical treatment to induce the labour.
- Caesarean section; defined as surgical delivery of baby (emergency or elective)
- Instrumental delivery; defined as an assisted birth when forceps or a ventouse suction cup is applied
- Retained placenta: as reported in medical records.
- Haemorrhage: 3rd stage of labour and immediate postpartum period, measured in ml blood loss; as reported in medical records.
- Maternal infection: as reported in medical records.
- Fetal growth: measured at 2nd and 3rd trimester scans, including:
 - o 2nd trimester scan: Fetal head circumference; Fetal abdominal circumference; Fetal Femur Length; Estimated fetal weight Hadlock; as reported in medical records.
 - o 3rd trimester scan: abdominal circumference; Femur Length; Estimated fetal weight Hadlock; Umbilical artery PI; End Diastolic flow; Amniotic Fluid Index; as reported in medical records.
- Large for gestational age; defined as birth weight above the 90th centile for gestational age and sex on INTERGROWTH chart.
- Small for gestational age; defined as birth weight below the 10th centile for gestational age and sex on INTERGROWTH chart.

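### The sample is shown to be adequate for pre-eclampsia only; the claim that every other outcome needs fewer women does not follow, because it ignores the anticipated C-index

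*Protocol*

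**What the plan says.** Section 8e (Sample size) states: "A sample of 1400 women will be recruited to the study". It says that recent sample-size methods for prediction models confirm this number as sufficient for the study. The inputs are "a maximum of 7 variables being included in the model", and "the least common pregnancy outcome, which is preeclampsia", with "estimated prevalence of approximately 5-6% of pregnancies in the UK". At a C-index of 0.80 and shrinkage of at most 10%, the minimum is given as 980 for pre-eclampsia. The remaining outcomes are covered by one sentence: "Given that other outcomes are more prevalent than pre-eclampsia, they would require sample sizes smaller than the above figure".

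Section 8f lists about 20 outcomes. Inside the pre-eclampsia entry it adds: "Early onset defined as onset of PE before 34 weeks gestation". Section 8g plans a separate multiple logistic regression for each outcome if no single adiposity measure outperforms BMI. It states that predictors are fixed in advance and that no variable selection will be done.

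The protocol gives no prevalence and no anticipated C-index for any outcome other than pre-eclampsia.

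**The concern.** The sentence reasons from prevalence alone. In the cited method, the number needed to hold shrinkage at a target depends on how much outcome variation the model explains (Cox-Snell R²), and that depends on both prevalence and discrimination. A common outcome that is hard to predict can need more women than a rarer one that is predicted well. The inference therefore holds only if every other outcome is at least as common as pre-eclampsia and is predicted about as well. The protocol states neither.

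The premise also sits badly with section 8f. Early-onset pre-eclampsia is a subset of pre-eclampsia, so it cannot be more common, and it is rarer unless every case is early.

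At stake is the statement that 1400 suffices for the whole study. For an outcome with a low C-index, a seven-parameter model would miss the protocol's own shrinkage target. With predictors fixed, section 8g offers no stated way to reduce the model for such an outcome.

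**Working it through.** **Inputs from section 8e.** P = 7 variables, taken as 7 parameters; prevalence 5-6%; C = 0.80; planned n = 1400; stated minimum 980. The target begins "Targeting a shrinkage factor of" and goes on to at most 10%; I read it as at most 10% shrinkage, that is, a shrinkage factor S = 0.90. All other prevalences and C values below are assumptions, because the protocol gives none.

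**Method.**
1. Convert C and prevalence to Cox-Snell R² by numerical integration, with a normal linear predictor in each outcome group and mean difference √2·z(C). At C = 0.80 this difference is 1.190.
2. N = P / [(S − 1)·ln(1 − R²/S)].

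**Reproducing the plan's figure.** At 5% and C = 0.80, R² = 0.0623. Then R²/S = 0.0692, ln(1 − 0.0692) = −0.0717, and N = 7 / (0.1 × 0.0717) = 976. At 5.5% it is 895 and at 6% it is 828. The method's other two criteria (0.05 optimism in Nagelkerke R²; ±0.05 on overall risk) give 411 and 73 at 5%, so shrinkage governs. The stated 980 is confirmed at the lower end of the prevalence range.

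**Other outcomes, same P and S, N rounded up.** The last column is the S that solves the same formula with N = 1400.

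| Prevalence (assumed) | C (assumed) | R² | N needed | Expected S at 1400 |
|---|---|---|---|---|
| 10% | 0.80 | 0.1115 | 530 | 0.960 |
| 10% | 0.70 | 0.0470 | 1,304 | 0.906 |
| 10% | 0.65 | 0.0260 | 2,388 | 0.841 |
| 15% | 0.65 | 0.0365 | 1,694 | 0.882 |
| 20% | 0.65 | 0.0453 | 1,355 | 0.903 |
| 20% | 0.60 | 0.0201 | 3,096 | 0.803 |
| 30% | 0.65 | 0.0587 | 1,039 | 0.924 |

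Only the first row supports the quoted sentence. In every other row the outcome is at least 10/6 = 1.7 times as common as pre-eclampsia, yet N exceeds 980. In three rows it also exceeds 1400.

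**What 1400 supports with seven parameters.** Setting N = 1400 and solving for C:

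| Prevalence | Smallest C | Rounded up |
|---|---|---|
| 5% | 0.757 | 0.76 |
| 6% | 0.739 | 0.74 |
| 10% | 0.693 | 0.70 |
| 20% | 0.648 | 0.65 |
| 30% | 0.630 | 0.63 |

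**Rarer outcomes.** At C = 0.80, N = 1400 corresponds to a prevalence of 3.39%. Early-onset pre-eclampsia falls below this if early cases make up less than 3.39/6 = 56% to 3.39/5 = 68% of all pre-eclampsia. The protocol does not give that share.

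**The case against.** The strongest reply is that the plan recruits 1400 against a minimum of 980, a margin of 1400/980 = 1.43, or 43%. At the protocol's own C of 0.80, that covers any binary outcome of about 3.4% prevalence or more. At 20-30% prevalence it covers C down to about 0.63-0.65. Some of the misses are also small: 15% prevalence at C = 0.65 gives an expected shrinkage factor of 0.882 against 0.90. All this stands, and it limits what can be concluded.

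A reader might infer that 1400 is too small for most listed outcomes. The documents do not support that, since the shortfalls above appear only at C values I assumed. A reader might also infer that retained placenta or maternal infection is rarer than pre-eclampsia. The protocol gives no rate for either, so this cannot be settled from it.

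On early onset, the definition sits inside the pre-eclampsia entry. It is not a separate outcome in the section 5 summary or in Appendix 2, and no separate model is promised. The conflict therefore arises only if early onset is modelled in its own right.

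It can also be said that section 8g uses multivariable models only if no single measure beats BMI, that it plans bootstrap optimism correction, and that section 11 plans later validation in individual participant data. These steps would measure overfitting and could correct for it. They do not make the sentence in section 8e valid. Finally, outcomes not binary as defined (fetal growth, Apgar scores, blood loss in ml) fall outside this calculation, so neither the plan's sentence nor the figures above speak to them directly.

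**Conclusion.** The concern holds in a limited form. The sample is shown to be adequate for pre-eclampsia at C = 0.80, and the protocol's 980 is correct for that case. The extension to all other outcomes is not a valid deduction under the cited method, because it leaves out the C-index. For a 10% outcome the required number runs from 530 at C = 0.80 to 2,388 at C = 0.65, so the missing input decides the answer. Adequacy for the other outcomes is asserted, not calculated.

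That is different from showing 1400 to be inadequate for any particular main outcome, which the documents cannot do. The figures assume S = 0.90, one parameter per variable, and a normal linear predictor. N is proportional to the number of parameters, so the spline or fractional-polynomial terms contemplated in section 8g would raise every N if they add parameters. The sentence should be corrected before models are fitted; it does not undermine the recruitment target.

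**What to change.** In section 8e, delete the sentence about other outcomes and limit the sufficiency statement to pre-eclampsia at the stated inputs. Drop or qualify the description of pre-eclampsia as the least common outcome, and say whether early onset will be modelled separately.

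In its place, state the pairs that 1400 supports with seven parameters: 5% with C of at least 0.76, 6% with 0.74, 10% with 0.70, 20% with 0.65, and 30% with 0.63.

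For binary outcomes whose observed events and anticipated C fall outside these pairs, either use fewer parameters or report single-measure c-indices with intervals. Because N is proportional to P, the number of parameters supported is 7 × 1400/N: 7 × 1400/2,388 = 4.1, so four, at 10% and C = 0.65; and 7 × 1400/3,096 = 3.2, so three, at 20% and C = 0.60. A fixed prevalence cut-off of 3.4% should not be used as the rule, since it applies only at C = 0.80.

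The cost is some wording and a short table. Fewer outcomes may receive a full seven-parameter model. No extra recruitment is needed.

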Pregnant and postnatal women and the Research Design Service North East and North Cumbria consumer panel were involved in the development of the proposed research funding application, protocol, and in planning future PPI activities as part of this research. A detailed overview of the patient and public involvement is provided in section 10 of the protocol.

5. Protocol Summary

Short title:	SHAPES Cohort Study
Protocol version:	1.0
Protocol date:	05/05/2017
Chief investigator:	[name]
Sponsor:	NUTH NHS Trust
Funder:	NIHR
Study design:	Prospective Cohort
Research question:	Are there alternative adiposity measures to BMI which better predict adverse pregnancy outcomes?
Study aim:	To evaluate the prognostic performance of single adiposity measures or a multivariable model to estimate risk of adverse pregnancy outcomes.
Study objectives:	
1. To identify the prognostic value of single adiposity measures for predicting adverse maternal, fetal and neonatal outcomes (for each outcome of interest separately, and as a composite outcome)2. To develop a prognostic model to investigate the effect of including multiple adiposity, socio-demographic and clinical predictors on the accuracy of predicting outcomes3. To test the predictive performance of the prognostic measures/models using calibration, discrimination and internal validation techniques

Adiposity exposure measures: *Subcutaneous abdominal fat; Visceral abdominal fat; Waist circumference; Hip circumference; Height; Weight; Neck circumference; Mid upper arm circumference; Skinfold thicknesses.*

Outcomes: *Gestational diabetes*
Gestational hypertension
Preeclampsia
Retained placenta
Haemorrhage
Maternal infection
Metabolic syndrome
Pre-term birth
Late-term birth
Induction of labour
Caesarean section
Instrumental delivery
Fetal growth
Large for gestational age
Small for gestational age
Apgar scores
Jaundice
Respiratory distress
Feeding method
*Admission to neonatal special care baby unit (SCBU) or intensive care unit (NICU), **high-dependency care, transitional care***

Number of study sites: *One*

Study population/size: 1400 pregnant women

Study duration: *Four years*

6. Background

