There is a high variation in individual phenotype makes BMI a poor predictor of adiposity-level and risk, especially among women and some ethnic groups (14). Meta-analysis of studies in non-pregnant populations shows that using obese BMI criteria only identifies 50% of adults with excess adiposity, as BMI cannot distinguish between fat mass and lean mass, whereas measures of body fat distribution can distinguish individuals' mortality and cardiometabolic risk (15, 16).

Failure to predict pregnancy risk results in harm for mother and child and increases healthcare costs. Furthermore, inaccurate risk communication can increase anxiety and distress, as well as waste care. There is an urgent need to identify measures of adiposity-related risk with greater sensitivity and specificity than BMI to inform targeted high-risk care to improve health of women and offspring and reduce waste of NHS resources.

This prospective cohort study will measure alternative (to BMI) indicators of obesity/adiposity in pregnant women to explore the ability of these markers to predict adverse pregnancy outcomes. A range of alternative adiposity measures exist, which can be assessed using a number of different anthropometric measures (for example, waist circumference, neck circumference) or ultrasound/MRI scans (for example to identify abdominal subcutaneous and visceral fat volumes). Some of these measures (e.g. MRI scans) are costly and impractical for implementation into routine pregnancy care. This study will focus on the measurement of indicators of obesity that it would be feasible to implement in routine NHS maternity care.

This study is one part of a larger body of work that seeks to address the question of if there are more cost-effective adiposity measures than BMI to allocate high-risk care in pregnancy.

7. Research question, aim and objectives

Are there alternative adiposity measures to BMI which better predict adverse pregnancy outcomes?

Aim

To evaluate the prognostic performance of single adiposity measures or a multivariable model to estimate risk of adverse pregnancy outcomes.

Objectives

1. To identify the prognostic value of single adiposity measures for predicting adverse maternal, fetal and neonatal outcomes (for each outcome of interest separately, and as a composite outcome)
2. To develop a prognostic model to investigate the effect of including multiple adiposity, socio-demographic and clinical predictors on the accuracy of predicting outcomes

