- Neck circumference, measured immediately superior to the thyroid cartilage and perpendicularly to the long axis of the neck with the head in the Frankfort plane, to the nearest 0.1 centimetre.
- Mid upper arm circumference, measured at the midpoint of the upper arm between the acromiale and radiale, perpendicular to the long axis of the arm, to the nearest 0.1 centimetre.
- Skinfold thicknesses (subscapular, triceps, biceps, iliac crest and supraspinale) measured using Harpenden skinfold callipers. Sum of skinfolds will be calculated using these measurements.
- Waist to hip ratio, waist to height ratio, BMI, Body Adiposity Index, A Body Shape Index (ABSI), Hip Index, Weight-Adjusted Waist Index, Body Roundness Index, Abdominal Volume Index, Conicity Index, Estimated Total Body Fat, Relative Fat Mass, CUN-BAE and body fat percentage will be calculated from these measurements. If any additional composite adiposity measures/indices become available in the literature that can be calculated by the data we have collected then we will explore whether to include these in our analysis.
- Self-reported body shape using a visual scale for body shapes

Measurements will be taken, directly on the skin unless otherwise specified above, on the right side of the body unless impracticable due to injury in which case the left side may be used. All anthropometric measurements will be taken by individuals who have received ISAK training (<https://www.isak.global/>). Measurements will be taken

in duplicate, and a third measurement undertaken if the difference between the first two measures is greater than 5% for skinfolds or 1% for other measures. If two measures are taken, the mean value will be used in data analysis. If three measures taken, the median value will be used.

Other predictor variables

A number of other variables that have previously been reported to be associated with pregnancy outcome will be collected by questionnaire or from routine records:

- a. Socio-demographic:
 - a. maternal age
 - b. parity
 - c. ethnic group
 - d. Index of Multiple Deprivation score (derived from postcode)
- b. Clinical:
 - a. This pregnancy/booking data (e.g. blood pressure, smoking, alcohol consumption)
 - b. Past obstetric history (previous gestational diabetes (GDM), pregnancy hypertension, caesarean section, macrosomia)
 - c. Other medical history (pre-existing type 1/type 2 diabetes, hypertension, bariatric surgery)
 - d. Family history of diabetes

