- Apgar scores at 1 and 5 minutes (score 1-10); as reported in medical records.
- Jaundice: as reported in medical records.

- Respiratory distress (including requiring resuscitation): as reported in medical records.
- Feeding method (first feed and feed method at discharge): breastfeeding or artificial feed; as reported in medical records.
- Admission to neonatal special care baby unit (SCBU) or intensive care unit (NICU), high-dependency care, transitional care; as reported in medical records.

In addition, information on any reason for loss to follow up (e.g. late miscarriage, stillbirth, or participant moving to another area) will be sought from medical records in order to account for missing outcome data.

g. Analysis

The aim of the analysis is to explore if any single adiposity measure taken in this study performs better than BMI in terms of predicting women at high-risk of an adverse pregnancy outcome. Each adiposity measure will be assessed individually. If no one measure performs better than BMI, multiple logistic regression models will be used for the analysis of each outcome separately. There won't be any variable selection since our predictors are already fixed. Wherever possible, we will retain continuous candidate predictors in their continuous form to avoid statistical power loss (29). Nonlinear trend in continuous predictors will be explored using either fractional polynomials or restricted cubic splines.

The apparent performance of the developed model will be summarised using calibration, discrimination and internal validation analyses (30). Calibration determines performance in terms of the agreement between the probability of developing the outcome as estimated by the measure/model, and the observed outcome frequencies. Discrimination is the measure of the model's ability to distinguish between individuals who develop the outcome or not (i.e., a higher probability assigned to the individual who develops the outcome compared with an individual who does not. This will be assessed using the c-index (equivalent to the area under the receiver operating characteristic [AUROC] curve).

Any missing values will be assumed to be missing at random (MAR) and multiple imputation (MI) will be implemented using 20 imputations (31). Calibration and discrimination of the developed model(s) will be summarised in the datasets

(averaged over imputation datasets). Calibration will also be assessed graphically (32).

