Appendix 1: Participant recruitment process

Appendix 2: Data items

Data item	Reason needed (if not predictor or outcome)	Source		
		Measured	Electronic records	From notes
Mother's NHS number	For data linkage		x	
Mother's name	For data linkage		x	
Mothers date of birth	For data linkage		x	
Maternal death	For data linkage/reason for missing outcome variables		x	
Infant date of birth	For data linkage		x	
Infant name if known	For data linkage		x	
Infant NHS number	For data linkage		x	
Predictor variables				
Height at research visit	n/a	X (12 weeks)	X (at booking)	x
Weight at research visit	n/a	X (12 weeks)	X (at booking)	x
Waist circumference	n/a	X (12 weeks)		
Hip circumference	n/a	X (12 weeks)		
Subcutaneous fat	n/a	X (12 weeks)		
Visceral fat	n/a	X (12 weeks)		
Pre-peritoneal VAT	n/a	X (12 weeks)		
Pre-peritoneal SAT	n/a	X (12 weeks)		
Neck circumference	n/a	X (12 weeks)		
Mid upper arm circumference	n/a	X (12 weeks)		
Skinfold thicknesses	n/a	X (12 weeks)		
Self-reported body image	n/a	X (12 weeks)		
Age at booking	n/a	x	x	x
Gravidity	n/a	x	x	x
Parity	n/a	x	x	x
Ethnic group	n/a	x	x	x
Postcode	To link to Index of Multiple Deprivation (IMD)	x	x	x
Blood pressure at booking systolic	n/a		x	x
Blood pressure at booking diastolic	n/a		x	x
Smoking status (in the past 12 months and current smoking)	n/a	x	x	x
Alcohol intake (before pregnancy and current intake)	n/a	x	x	x
Substance use (before pregnancy)	n/a	x	x	x
Previous C-section	n/a		x	x
Previous macrosomia	n/a		x	x
Diabetes history	n/a		x	x
Family history of diabetes	n/a		x	x
Previous spontaneous preterm birth or mid trimester loss between 16+0 and 34+0 weeks gestation	n/a		x	x
Cervical trauma	n/a		x	x
Cervical length < 25 mm	n/a		x	x
Family history of preeclampsia	n/a		x	x
Essential hypertension	n/a		x	x
Previous pregnancy hypertension	n/a		x	x
Chronic renal disease	n/a		x	x
Autoimmune disease	n/a		x	x
Last pregnancy >10 years ago	n/a		x	x
Previous low birth weight <10%	n/a		x	x

Data item	Reason needed (if not predictor or outcome)	Source		
		Measured	Electronic records	From notes
Previous still birth	n/a		x	x
Previous neonatal death within 4 weeks of life	n/a		x	x
Previous bariatric surgery	n/a	x	x	x
Congenital anomaly	n/a		x	x
Maternal folic acid supplementation	n/a		x	
Outcome measures				
Diagnosis of GDM from home glucose monitoring	GDM			>32 w
OGTT Fasting blood glucose	GDM		< 32 w	
OGTT fasting insulin	GDM/Metabolic Syndrome		< 32 w	
OGTT 1 hour post 75g glucose challenge glucose	GDM		< 32 w	

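### The metabolic syndrome outcome contains a BMI-or-waist item taken from the same early-pregnancy measurements that are being compared, so the comparison with BMI is biased for this outcome

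*Protocol*

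**What the plan says.** Section 8f (Outcomes) states that metabolic syndrome is "diagnosed using 3 of the following measures: overweight/obese BMI or high waist circumference, elevated triglycerides". The list ends with "high blood pressure that's consistently 140/90mmHg or higher, insulin resistance". That makes four items, three of which are required. BMI and waist are alternatives within one item.

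Waist is also an exposure. The Protocol Summary (section 5) lists "Subcutaneous abdominal fat; Visceral abdominal fat; Waist circumference; Hip circumference; Height; Weight; Neck circumference" among the adiposity measures, and section 8f derives "Waist to hip ratio, waist to height ratio, BMI, Body Adiposity Index, A Body Shape Index (ABSI), Hip Index" and further indices from the same visit. BMI is the benchmark: section 8g sets out to "explore if any single adiposity measure taken in this study performs better than BMI". Objective 1 in section 7 applies the measures "for each outcome of interest separately, and as a composite outcome", and metabolic syndrome is not exempted.

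Appendix 2 tags two laboratory items for this outcome, "OGTT fasting insulin" and triglycerides, both from the glucose tolerance test. Height and weight are listed as research-visit items, with booking values from electronic records. Waist is listed at 12 weeks only. Section 12 says that women are not contacted again after that visit.

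**The concern.** The same measurement stands on both sides of the model. The BMI that is scored as a predictor also decides, for many women, whether they count as a case. This is incorporation bias: BMI and waist would discriminate for this outcome even if they had no relation to triglycerides, blood pressure or insulin resistance.

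The study asks whether other measures do better than BMI, so an advantage built into BMI bears directly on that question. Ultrasound fat, neck, arm and skinfold measures get credit only through their correlation with BMI or waist. Indices built from BMI or waist share the credit in varying degree. Section 8g moves to multivariable models if no single measure beats BMI, so for this outcome the bias can also influence that step. The planned bootstrap does not remove it. It corrects overfitting, and every resample carries the same outcome definition.

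**Working it through.** The protocol gives no figure for this outcome. Its one computed design figure, 980 women for preeclampsia, does not enter here.

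**Inputs.** From the protocol: 21% obese plus 28% overweight (section 6), so 49% meet the BMI part of the item; three of four items required (section 8f). Everything else is assumed: high waist in 30–50% of women, the prevalence of the other three items, and all correlations.

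**Step 1: the structure.** Let A mean that the BMI-or-waist item is met, and k be the number met among the other three. A woman is a case if k = 3, or if k = 2 and A. So A is not sufficient (k must be at least 2) and not strictly necessary (k = 3 qualifies without it), but it lowers the bar from three items to two.

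**Step 2: a hand calculation, simplified.** Take BMI of 25 or more as the only route to A, with the other items independent of BMI and of each other. Within each BMI group BMI then carries no information, so

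c-index = 0.5 + (w1 − w0)/2,

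where w1 and w0 are the shares of cases and non-cases with A. Assume triglycerides 20%, blood pressure 10%, insulin resistance 20%.

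- P(k = 2) = 2 × (0.2 × 0.1 × 0.8) + 0.2 × 0.2 × 0.9 = 0.068
- P(k = 3) = 0.2 × 0.1 × 0.2 = 0.004
- P(case) = 0.49 × 0.072 + 0.51 × 0.004 = 0.0373
- w1 = 0.0353/0.0373 = 0.945
- w0 = 0.49 × 0.928/0.9627 = 0.472
- c-index = 0.5 + (0.945 − 0.472)/2 = 0.736

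BMI has no true association here, yet scores 0.736. This is not the figure to rely on. It leaves out the waist alternative and treats the other items as independent, and both choices raise it.

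**Step 3: the definition as written.** Multivariate-normal simulation, 1,000,000 women per scenario. A is met by BMI or by waist. Assumed: BMI–waist correlation 0.85; another adiposity measure correlated 0.7 with each; 0.25 among the other three items; triglycerides and insulin resistance 20–30%, blood pressure 10%. With the item removed, a case is at least two of the remaining three.

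| True correlation of adiposity with other items | BMI | Waist | Other measure | All, item removed | BMI minus other, as written |
|---|---|---|---|---|---|
| 0 | 0.66–0.70 | 0.66–0.67 | 0.62–0.63 | 0.50 | 0.045–0.063 |
| 0.15 | 0.73–0.76 | 0.73–0.74 | 0.69–0.71 | 0.60–0.61 | 0.034–0.055 |
| 0.30 | 0.79–0.81 | 0.79–0.80 | 0.76–0.77 | 0.70–0.71 | 0.025–0.044 |

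In these scenarios 87–98% of cases meet the adiposity item, and for 74–83% it is the item that completes the three.

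**Step 4: wider assumptions.** Let the other items be independent or correlated 0.25, let blood pressure fall to 5%, and add a setting with triglycerides 80%, blood pressure 10% and insulin resistance 50%.

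- No true association: BMI about 0.66–0.77, waist 0.66–0.74, other measure 0.62–0.68; BMI 0.50 with the item removed. About 87–97% of cases meet the item.
- True correlation 0.15–0.30: BMI inflated by about 0.06–0.23, with an edge of about 0.02–0.08 over the equally informative outside measure.

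**The case against.** The strongest reply is that the damage is limited. Metabolic syndrome is one of about 20 listed outcomes and is not designated primary. The sample size rests on preeclampsia, and outcomes are analysed separately, so the others are untouched. For measures outside the definition the bias works against declaring them better than BMI, so a win over BMI would be credible. Waist against BMI is roughly neutral when high waist is about as common as overweight. All of this stands, and it limits the severity.

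Four stronger readings are tempting but not supported.

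- A reader might infer that the comparison is decided in advance. It is not. With BMI and waist correlated 0.15 with the other items and an outside measure correlated 0.25, the outside measure still came out ahead, 0.76 against 0.73 (triglycerides and insulin resistance 20%, blood pressure 10%, high waist 50%, 0.25 among the items). With prevalences of 80%, 10% and 50% it fell just behind, 0.76 against 0.77. The comparison is tilted, and a modest true advantage can be lost.
- A reader might infer that nearly all cases have BMI of 25 or more by definition. A woman can qualify through waist, or on the other three items alone.
- A reader might take 0.50 as BMI's true performance. That is only the null scenario. The protocol's own premise, in sections 6 and 8d, is that body fat distribution relates to cardiometabolic risk, and under a real association the inflation is smaller.
- A reader might infer that the composite is contaminated. The protocol does not say which outcomes form it, so this is conditional.

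None of this removes the overlap. The definition is fixed in the protocol, and nothing in the document acknowledges or handles it.

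**Conclusion.** The concern holds in a limited form. As written, the metabolic syndrome outcome gives BMI and waist, and to a varying degree indices built from them, discrimination that they have not earned, and handicaps measures outside the definition against the benchmark. The direction follows from the definition and the data list alone.

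The size depends on assumptions, since only the 49% share is documented; the ranges in steps 3 and 4 show rough magnitude and are not estimates for this cohort. An edge of about 0.02 to 0.08 in c-index is enough to hide a modestly better measure. The finding also rests on the adiposity item being scored from booking or 12-week values, which is all that Appendix 2 lists.

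This should be fixed before outcomes are analysed. It does not undermine the study as a whole.

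**What to change.** For the prognostic comparison, define this outcome on triglycerides, blood pressure and insulin resistance only, either as at least two of the three or as three separate outcomes. Otherwise, take metabolic syndrome out of the comparison with BMI and out of any composite, and report it descriptively.

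The change is about one sentence in section 8f and needs no new data. Make it before outcomes are analysed, because a definition chosen after seeing results would carry little weight. The cost is that the analysed outcome is no longer conventional metabolic syndrome and needs another label, such as metabolic abnormality excluding adiposity. This concerns the analysis definition only and does not touch clinical diagnosis or care.
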